- 41. Bleicher RJ. Timing and Delays in Breast Cancer Evaluation and Treatment. Ann Surg Oncol. 2018 Oct;25(10):2829-2838. doi: 10.1245/s10434-018-6615-2. Epub 2018 Jul 2.
- 42.https://www.cancer.org/es/tratamiento/tratamientos-y-efectos-secundarios/tipos-de-tratamiento/q uimioterapia/como-la-quimioterapia-es-usada-para-tratar-el-cancer.html

OBJECTIVES

GENERAL OBJECTIVES

- I. Determine a preliminary exploration of the magnitude of the effect of a kinesitherapy and stretching intervention for the functional recovery of the upper limb, the recovery of the surgical scar and the improvement of the quality of life in women who have suffered from breast cancer.
- II. Create a scale to objectively classify the axillary thrombus (based on its clinical manifestations).

SPECIFIC OBJECTIVES for general objective I:

- Check the intervention of assisted passive kinesitherapy and stretching for the improvement of the range of joint mobility of the affected limb in the shortest possible time.
- Analyze the reduction of pain and increase of the degree of functionality of the ipsilateral upper limb in patients with AWS after the intervention.
- -Determine the impact of the physiotherapeutic intervention on the quality of life of a mastectomized woman with lymphatic thrombus.
- -Analyse the physiotherapeutic intervention reduction of the time on the evolution of the Superficial Lymphatic Thrombus and the application of Radiotherapy within the terms established in the oncological protocols.

SPECIFIC OBJECTIVES for general objective II:

- Create a scale to objectively classify the axillary thrombus (based on its clinical manifestations).

METHODOLOGY

TYPE OF STUDY

Quasi-experimental, prospective study.

STUDY POPULATION

The study sample is made up of patients undergoing surgery for Breast Cancer who attend the Lymphedema Unit of the A.G.S. Campo de Gibraltar Oeste presenting Lymphatic Thrombus after the operation, the recruitment period being from December 2021 to December 2023.

CALCULATION OF SAMPLE SIZE

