To calculate the sample size, the prevalence of axillary network syndrome (AWS) described in the scientific literature was taken into account. It affects 30%. The 2020 records for patients who attended the Lymphedema Unit of A.G.S. Campo de Gibraltar Oeste has also been included adding 83 new patients. With these figures, a random sample of 46 individuals in total would be enough to estimate, with a 95% confidence and a precision of +-5 percent units, a population percentage of 10%.

SELECTION CRITERIA

Patients who meet all the inclusion criteria and no exclusion criteria will be included in this study prospectively.

INCLUSION CRITERIA

- Patient over 18 years old.
- Mastectomized patients (either radical or conservative surgery).
- Patient with lymphatic thrombus in the upper limb ipsilateral to the surgical intervention.

EXCLUSION CRITERIA

- Significant psychological alterations that would prevent the retrieval of the information necessary for the investigation.
- Significant neurological alterations that would prevent the retrieval of the information necessary for the investigation.
- Patients in a situation of legal dispute that would affect their intervention in this study.
- Metastasis not treated with chemotherapy treatment.

WITHDRAWAL CRITERIA

- Withdrawal of informed consent from the patient.
- Administrative decision taken by the researchers, promoter or a regulatory authority.
- Mild adverse event.
- Serious, unexpected or clinically relevant adverse event.

VALUATION CRITERIA

Main Variables:

- Mobility of the affected shoulder, measured by goniometry.
- Functionality assessment using the Constant and DASH scale (29,30).

Secondary variables:

Sociodemographic and clinical-surgical variables

- Age
- Marital status: married or in a common-law relationship, widowed, divorced or separated, single.
- Level of completed studies: illiterate, primary studies, secondary studies, university studies.
- Type of residence: in an urban / rural area.

- Children: yes / no.
- Mother after 30 years old: yes /no.
- Smoker: yes /no.
- Type of cancer. Four categories have been assessed: ductal, infiltrating, in situ, Paget's.
- Number of lymph nodes removed.
- Type of surgery (radical-conservative).
- Breast reconstruction (yes / no).
- Radiotherapy (yes / no).
- Time from surgery to the appearance of the Lymphatic Thrombus in days.

Clinical Variables:

- Visual Analog Pain Scale.
- Goniometry of all joints of the affected upper limb.

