Axillary cord syndrome: It is a nominal qualitative variable. The presence of lymphatic cord was assessed by observation and palpitation by the assessor. Physical exam performed as suggested in previous researches: patient laying in supine position with elbow extended and the shoulder in maximum abduction. The assessor observes and palpates the beads, including the armpit, down the upper arm from the armpit to the antecubital space and through the forearm to the base of the thumb (34).

Range of motion: It is a continuous quantitative variable. For the assessment of the mobility goniometry has been used. Goniometer is the standard instrument for measuring the range of movement. The patients were asked to move thir arms in flexion, extension, abduction and external and internal rotation of the shoulder. It was considered that the maximum range of motion for the

flexion and abduction was 180°, for extension it was 45°, 100° for internal rotation and 80° for external rotation. Finally, a single index was calculated as the percentage of global movement (). Constant Scale: According to the Spanish Society for Shoulder and Elbow Surgery (SECHC), the Constant Scale assesses pain, functionality for daily life activities, joint mobility and shoulder strength. Also, it considers the laterality and the time it takes the patient. The score ranges from 0 points to 100 points, being 100 the optimal condition for the shoulder. (35, 37).

Quick-Dash (DASH): The Disabilities of the Hand, Arm and Shoulder (DASH) questionnaire is a specific instrument for measuring the quality of life related to health problems to the upper limbs. It is validated in Spanish and it consists of 30 questions. The final score calculation is relatively complicated. In order to calculate the scores it is necessary to have answered at least 27 out of the 30 questions. The final scores is obtained by calculating the arithmetic means of the questions answered minus 1 times 25. The DASH questionnaire has excellent reproductibility and high sensitivity, being able to detect small changes. The scale ranges from 30 to 150 points. 30 points means good shoulder functionality and 150 non-functional shoulder

It has two optional subsections where sports and work functionality can be assessed (38).

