Visual Analog Pain Scale (VAS): According to the National Cancer Institue (NIH), it is a tool used to help the professional assess the intensity of certain sensations and feelings, such as pain. The Visual Analog Scale for pain is composed of a straight line on which an extreme means no pain and the other extreme means the worst pain imaginable. Extreme pain corresponds to 10 points. None pain corresponds to 0 points.

The patient marks a point on the line that matches the amount of pain they feel. Also known as VAS (36).

International Scale of Physical Activity (IPAQ): The main use of the IPAQ (International Physical Activity Questionnaire) worldwide is aimed at monitoring and investigation purposes. It is an instrument designed mainly for the "monitoring" of physical activity performed by the adult population and their perception of their health. Its aim is to learn about the kind of physical activity that people do as part of their daily activities. The questions are focused on the time the patient spends being physically active during the previous 7 days. The patient should consider the activities he/she does as part of work, garden, at home, leisure, moving from one place to another during their rest, exercise or sport.

IPAQ is scored by comparing the OMS recommendations. For the group of adults from 18 to 64 years old, it is done as follows: perform at least 150 minutes per week of moderate physical activity, or 75 minutes per week of vigorous physical activity, or an equivalent combination of both, that is, between both intensities they add up to at least 150 minutes of physical activity per week. The patient must answer each question in minutes a week (39).

EORTC-QLQ-BR23 questionnaire: It consists of a validated questionnaire consisting of 30 questions. The first 28 questions are scored from 1 to 4, with the highest values being those that show greater difficulty when carrying out the activity for which they are asked or the worst state of health. 126 points is the highest score and means excellent health. 0 points means the worst health.

Finally, there are two general questions about the state of health and quality of life that score from 1 to 7, the highest value being the best state of health and quality of life. The vast majority of questions refer to the previous week (40).

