Annex 2. DASH scale

DASH SCORE _____

 Patient Name
 DOB
 DOS
 DOE

 Preop
 2 week F/U
 6 week F/U
 12 week F/U

[figure not shown]
 6 month F/U
 12 month F/U
 24 month F/U

	No difficulty	A little difficulty	Moderate difficulty	A lot of difficulty	I wasn't able to do it
1. Open a new glass jar, or one with a very tight lid	1	2	3	4	5
2. Write.	1	2	3	4	5
3. Turn a key	1	2	3	4	5
4. Prepare a meal	1	2	3	4	5
5. Open a heavy door	1	2	3	4	5
Put something on a shelf above head height	1	2	3	4	5
7. Do heavy domestic tasks (such as washing the floor)	1	2	3	4	5
Do gardening work	1	2	3	4	5
9. Make your bed	1	2	3	4	5
10. Carry a bag or a small case	1	2	3	4	5
11, Carry a heavy object (more than 5 kg).	1	2	3	4	5
12. Change a light bulb above head height	1	2	3	4	5
13. Wash or dry your hair	1	2	3	4	5
14. Wash your back	1	2	3	4	5
15. Put on a closed blouse	1	2	3	4	5
16. Use a knife to cut food	1	2	3	4	5
Recreational activities that require little effort (such as playing cards or knitting)	1	2	3	4	5
 Recreational activities that require strength or impact in the arms, shoulders or hands (such as playing volleyball or hammering) 	1	2	3	4	5
19. Recreational activities in which you move your arm freely (such as fishing or playing shuttlecock)	1	2	3	4	5
20. Transport from one place to another (going from one place to another)	1	2	3	4	5
21. Sexual activities	1	2	3	4	5
	It didn't affect them	It affected them slightly	It affected them moderately	It affected them a lot	It affected them enormously
22. Last week, to what extent did your arm, shoulder or hand problem affect your normal activities with your family, friends, neighbors or colleagues?	1	2	3	4	5
	It didn't limit them	It limited them alightly	It limited them moderately	It limited them a lot	I wasn't able to do them
23. Last week, were your work or normal daily activities limited because of your arm, shoulder or hand problem?	1	2	3	4	5
Rate how severe the following symptoms were last week	None	A little	Moderate	A lot	Extreme
24. Pain in your arm, shoulder or hand	1	2	3	4	5
25. Pain in your arm, shoulder or hand when you did specific activities	1	2	3	4	5
26. Discomfort in the skin of your arm, shoulder or hand (prickling)	1	2	3	4	5
27. Weakness in your arm, shoulder or hand	1	2	3	4	5
28. Difficulty in moving your arm, shoulder or hand	1	2	3	4	5
	No difficulty	A little difficulty	Moderate difficulty	A lot of difficulty	So difficult that

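### The stated DASH range (30 to 150) contradicts the stated DASH formula (0 to 100), and no scoring stated in the plan gives the quality-of-life anchors 0 = worst and 126 = excellent

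*Combined protocol and SAP*

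**What the plan says.** **DASH.** The Main Variables list names shoulder mobility by goniometry, and function by the Constant and DASH scales. The paragraph headed Quick-Dash (DASH), under Control Group, describes 30 questions, requires at least 27 answers, and gives the scoring rule: "The final scores is obtained by calculating the arithmetic means of the questions answered minus 1 times 25". Later in the same paragraph it states: "The scale ranges from 30 to 150 points. 30 points means good shoulder functionality and 150 non-functional shoulder". Annex 2 prints the 30-item form. Its first item, "Open a new glass jar, or one with a very tight lid", and all the others carry response codes 1 to 5, with 5 the worst.

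**Quality of life.** A specific objective is to determine the "impact of the physiotherapeutic intervention on the quality of life of a mastectomized woman with lymphatic thrombus". The paragraph on the EORTC-QLQ-BR23 describes 30 questions. On coding it says: "The first 28 questions are scored from 1 to 4, with the highest values being those that show greater difficulty". It adds two general questions "that score from 1 to 7, the highest value being the best state of health and quality of life". Its anchors are: "126 points is the highest score and means excellent health. 0 points means the worst health". It gives no rule for forming a total: no recoding, no subtraction, no rescaling.

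**Names.** The Control Group and Intervention Group sections say that Quick-DASH will be performed, but the description and Annex 2 are of a 30-item form. The annex list, the Result Variables list, the questionnaire paragraph and the Annex 6 title say QLQ-BR23. The annexed form is headed QLQ-C30 and has the 28 + 2 items described.

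**Use.** Analysis of Results plans the mean, median, mode, minimum and maximum of quantitative variables, overall and by type of treatment. Its only named tests are chi-square and Fisher, for pairs of qualitative variables.

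**The concern.** A score should have one definition, and its printed range and anchors should follow from it. For DASH, one paragraph gives two metrics. A reader who takes a formula score and interprets it by the printed anchors will misjudge function. Because the two ranges overlap from 30 to 100, a value there does not reveal which metric was used. General objective I is a preliminary exploration of the magnitude of an effect, so the unit of a main variable is part of the result.

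For quality of life, the item coding and the anchors point in different directions. If someone simply added the items and read the total by the printed anchors, worse health would appear as better health on an outcome tied to a stated objective.

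**Working it through.** **Inputs.** DASH: 30 items, at least 27 answered, formula and range (Quick-Dash (DASH) paragraph); codes 1 to 5 (Annex 2). Quality of life: 28 items coded 1 to 4, higher worse; two items coded 1 to 7, higher better; anchors 0 and 126 (EORTC-QLQ-BR23 paragraph; codes also on the Annex 6 form).

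**DASH: reproducing the stated range**
- Raw sum, 30 items answered: 30 × 1 = 30 to 30 × 5 = 150. This reproduces 30 to 150.
- Raw sum, 27 items answered: 27 × 1 = 27 to 27 × 5 = 135. A form that the plan accepts can therefore fall below the stated minimum.

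**DASH: the stated formula**
- (mean − 1) × 25: (1 − 1) × 25 = 0 to (5 − 1) × 25 = 100, whether 27 or 30 items are answered.
- Other readings of the sentence do not rescue the range. Mean − (1 × 25) gives −24 to −20. (Sum − 1) × 25 with 30 items gives 725 to 3725.

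**DASH: size of the conflict**
- For complete forms, raw sum = 1.2 × formula score + 30, so differences and standard deviations differ by a factor of 1.2.
- Value 30: on the formula, mean item 30/25 + 1 = 2.2; on the raw sum, 30/30 = 1.0, which is the best possible state.
- Formula scores from 0 to just under 30 (mean item 1.0 to just under 2.2) lie outside the stated range.
- Value 100: on the formula, mean item 100/25 + 1 = 5.0, the worst state; on the raw sum, 100/30 = 3.33. Read on 30 to 150, it sits at (100 − 30)/120 = 58.3% of the way to the worst.
- With a mean item of 3, the formula gives (3 − 1) × 25 = 50 for 27 or 30 answers. The raw sum gives 27 × 3 = 81 or 30 × 3 = 90, so omitted items look like better function.

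**Quality of life: possible scorings**

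| Scoring | Worst health | Best health |
|---|---|---|
| Sum as coded | 28×4 + 2×1 = 114 | 28×1 + 2×7 = 42 |
| Items 1–28 recoded 5 − x, then summed | 28×1 + 2×1 = 30 | 28×4 + 2×7 = 126 |
| Items 1–28 reversed, all items zero-based | 0 | 28×3 + 2×6 = 96 |

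- As coded, the total can run from 28×1 + 2×1 = 30 to 28×4 + 2×7 = 126. So 126 is reproduced as an arithmetic maximum, but it needs the worst answer on 28 items and the best on two. Zero cannot be reached.
- Of the span 28×3 + 2×6 = 84 + 12 = 96 points, 84/96 = 87.5% comes from items that run against the stated direction.
- A full change from worst to best is 42 − 114 = −72 as coded and 126 − 30 = +96 after recoding.
- Both anchors can be met by a rescaling, and more than one would do. Example 1: (recoded total − 30) × 126/96. Example 2: item by item, (4 − x) × 4/3 for items 1–28 and (x − 1) × 7/6 for items 29–30, giving 0 to 28×4 + 2×7 = 126. The plan states neither.

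**The case against.** The strongest reply on DASH is that the formula is explicitly the rule for the final score, so what will be computed is clear, and 30 to 150 is a loose description of the raw form. For complete forms the two metrics are exact linear transforms in the same direction, so ordering would not change, nor would a test unaffected by linear rescaling. No threshold, responder rule, sample-size input or planned test uses the 30 to 150 range. All of this stands, and it limits the consequence. It does not remove the contradiction: the text attaches its anchors to the scale without saying that they belong to the raw sum, and the raw sum does not fit the 27-of-30 rule.

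On quality of life, the reply is that the harm needs an unrecoded total. The plan prescribes no total at all, and calling 126 excellent suggests that recoding was intended. That also stands. A reader might infer that the quality-of-life result will come out reversed; the documents do not support that, because they leave the scoring open. Nor do they support saying that no scoring could meet both anchors, since some unstated rescalings do. Separately, the assessments named at arrival and days 30, 60 and 90 do not list the EORTC form, although all variables are to be recorded; this bears on timing, not on scoring.

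A reader might also infer from the names that the wrong forms are annexed. The documents show only that names and forms disagree. The item counts in the text match the annexed forms, but that does not settle which instrument was meant.

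**Conclusion.** The point holds and should be fixed. For DASH, the stated formula gives 0 to 100 and the stated range is 30 to 150; both cannot describe the same score. Direction is the same under both (higher is worse), so it would be too strong to say that the DASH effect could change sign. The error is in metric and anchors, on a main variable, with an overlap from 30 to 100 in which a number has two meanings.

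For quality of life, no scoring stated in the plan gives both 0 = worst and 126 = excellent. Summing as coded runs opposite to the stated direction (best 42, worst 114). Reversal of the conclusion is conditional on such a total being computed and read by the printed anchors. This part carries less weight than DASH, because it concerns an objective and a result variable, not a main variable.

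Since Analysis of Results specifies no between-group test of either score, the harm in both cases is to how reported values are labelled and read. The arithmetic assumes the item counts and codes in the text and annexes, and complete forms except where 27 answers are shown.

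**What to change.** **DASH.** Keep the formula, which already handles the 27-of-30 rule. State the range as 0 (best) to 100 (worst) and delete 30 to 150 with its anchors. Reconcile the name Quick-DASH with the 30-item form described in the text and printed in Annex 2.

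**Quality of life.** Delete the 0 and 126 anchors. Report the two global items (higher better) separately from the 28 problem items (higher worse), and say how the 28 are summarised. If a single total is kept, state that items 1–28 are first recoded as 5 − x, giving 30 (worst) to 126 (best) for complete forms, and state how missing items are handled. Reconcile the name QLQ-BR23, in the annex list, variable list, questionnaire paragraph and Annex 6 title, with the annexed form headed QLQ-C30.

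**Cost.** If the annexed forms are the intended instruments, this is text correction only, with no new data or visits. If Quick-DASH or QLQ-BR23 is the intended instrument, the corresponding annexed form and its scoring text must change.

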- Record of daily performance of lymphedema prevention kinesitherapy since the operation (days per week / duration in minutes / day).
- Approximate time elapsed since breast cancer diagnosis: years. Date format dd / mm / yy will be included, if possible.
- Stage in which the cancer is found, according to the TNM scale.
- Body mass index.
- Creation of a scale to classify the type of lymphatic thrombus (based on its location, length, thickness, pain, functional limitation and whether it is palpable-visible or not).

Result Variables:

- Level of physical activity measured by the International Physical Activity Questionnaire.
- -Quality of life questionnaire EORTC QLQ-BR23

Employment and leisure Variables:

- Employment situation at the time of data collection: Four categories have been assessed: Active / Retired / Unemployed / Home worker.
- Sport practice: yes / no.
- Sport and frequency.

Description of the intervention

15 sessions of Assisted Passive Kinesitherapy are carried out by the physiotherapist. Five days a week, for three weeks. If it is previously referred, the treatment will be finished earlier (the patient must achieve the same ranges of motion and strength as the contralateral limb, together with the remission of pain).

The stretches applied during the sessions will be gentle and maintained, never exceeding a pain grade 5 VAS (moderate pain), once the tension of the cord is reached between 20-30 seconds. A special effort will be made to recover flexion and abduction of the shoulder, bringing the cord to a tolerable tension on the part of the patient.

Friction will be made on the axillary scar to dislodge underlying planes and the subcutaneous tissue of the muscle fascia.

The patient will be trained in active kinesitherapy to prevent lymphedema and activate lymphatic circulation. Also with hygienic-postural measures for the same purpose.

CONTROL GROUP

All the variables and data for each patients are recorded in their clinical history. Goniometric study will be performed of the affected upper limb (shoulder, elbow, wrist). Constant scale, Quick-Dash, the Visual Analog Pain Scale and the International Scale of Physical Activity will also be performed. This assessment will be carried out the patient arrives at our unit and on day 30, 60, 90.

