The session will begin with pendulum exercises of the shoulder to warm up the joint and give proprioceptive stimulation to the joint capsule.

[figure not shown]
The physiotherapist will perform passive stretches looking to tensioning the lymphatic cord, never exceeding grade 6 VAS pain chart. Mainly the affected shoulder will be treated and if the cord reaches the crease of the elbow or thumb, the extension (frase sin sentido general hay que volverla a escribir).

Scar massage will be done in the area where the lymphatic cord originates at the proximal level while maintaining the tolerable tension of the lymphatic cord (during the massage also pain grade 6VAS will be exceeded).

Patients with developed lymphedema will receive Decongestive Physical Therapy (PDT) on the treated limb once the 15 day treatment described for the study is finished. Therefore, PDT does not influence on obtained contaminated results. Those patients who do not suffer from lymphedema do not receive PDT.

Manual Therapy, Scar Massage and exercises for the Intervention Group:

Exercise 4.- The Physiotherapist rests the affected limb diagonal to regular movement only if pain due to stretching is moderate.

Exercise 5.- The Physiotherapist rests the limb in shoulder flex following elbow extension.

[figure not shown]
Exercise 6.- The Physiotherapist places the limb in abduction position while patient can tolerate discomfort.

Exercise 7.- In case the cord reaches the elbow, the Physiotherapist holds the elbow extension combined with supination of the limb. The shoulder will be kept in flexed position as long as pain is moderate to keep the tension of the cord.

Exercise 8.- If the thrombus reaches the first finger, the Physiotherapist will try to reach the ulnar deviation of the wrist together with the flexion of the thumb. The shoulder will be kept in a flexed position and the elbow in an extended supination position.

ANALYSIS OF RESULTS

A descriptive analysis of all the variables included in the study will be presented at the overall level and by type of treatment in the Axillary Web Syndrome. For the qualitative variables, the relative and absolute frequencies will be presented. In the case of quantitative variables, summary statistics will be presented (mean, median, mode, minimum and maximum).

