For all study objectives in which two qualitative variables are related, the non-parametric Chi-square test will be used and, if necessary, the Fisher test will be used (in cases where the absolute frequency of more than 20% of the levels is less than 5 observations). To quantify the possible predisposing factors, the relative risk measures (RR), Odds ratio (OR) and their associated confidence interval will be obtained; Likewise, the sensitivity or specificity will be presented if it is considered necessary.

All analyzes will be accompanied by graphic representations for greater detail. Missing values will be those that are not completed.

All analyzes will be carried out with free R software and the significance level for all hypothesis testing is determined at 0.05.

WORKPLAN

The study will be carried out according to the following schedule:

Development and approval of the Provincial CEIC

OCTOBER 2021

Beginning of the recruitment period and action on the intervention group

DECEMBER 2021

Drafting of results, discussion and conclusions of the project

DECEMBER 2023

According to the schedule set forth, the research project will be completed in a period of 24 months.

The researcher [name] will register the patients, whether they are in the control group or in the intervention group. The physiotherapy intervention will be applied during 12 sessions from Monday to Friday to the selected patients.

The researcher [name] will be in charge of comparing the results with a double-blind system and thus comparing the results of the control group with the intervention group. The researcher [name] will be the methodological advisor in this research.

[name], with the help of [name] and [name] will write the results, discussion and conclusions of the project.

DISSEMINATION AND DISSEMINATION PLAN

- 1. Publication in journals indexed in the Journal Citation Report (JCR), in the field of Oncology and Rehabilitation and Physical Medicine and Physiotherapy.
- 2. Dissemination of results in national and international Congresses of Oncology and Rehabilitation and Physical Medicine and Physiotherapy.
- 3. Dissemination to the public, press releases and explanatory brochures of the project.
- 4. Dissemination on the website of the A.G.S. Campo de Gibraltar West.

ETHICAL ASPECTS OF THE RESEARCH

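### The intervention is specified inconsistently: two VAS ceilings for stretching, a scar-massage limit worded as its reverse, and 12 sessions in the workplan against 15 elsewhere

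*Combined protocol and SAP*

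**What the plan says.** Three features of the intervention are stated more than once, or unclearly, in the combined protocol and SAP.

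- **Pain ceiling for stretching.** Under *Description of the intervention*, stretches are held at cord tension, "never exceeding a pain grade 5 VAS (moderate pain"). Under *Intervention Group*, the physiotherapist's passive stretches of the same cord are "never exceeding grade 6 VAS pain chart".
- **Pain limit for scar massage.** Under *Intervention Group*, massage is given "while maintaining the tolerable tension of the lymphatic cord", and then: "during the massage also pain grade 6VAS will be exceeded".
- **Number of sessions.** *Description of the intervention*: "15 sessions of Assisted Passive Kinesitherapy are carried out by the physiotherapist", with the schedule "Five days a week, for three weeks". *Intervention Group* repeats 15 sessions at five days a week, about 40 minutes each, and times decongestive therapy for patients with lymphedema to begin "once the 15 day treatment described for the study is finished". *Workplan*: "The physiotherapy intervention will be applied during 12 sessions from Monday to Friday to the selected patients".

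*Description of the intervention* also lets a patient finish early once motion and strength match the other limb and pain has remitted.

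**The concern.** These are the instructions a physiotherapist would follow. Two absolute ceilings with different values cannot both be the limit, so staff cannot tell which one applies and a monitor cannot tell when it has been breached. Read literally, the massage sentence directs treatment past the ceiling that the same section sets for stretching.

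The session count fixes the planned maximum dose, which is part of what the study tests and what others would reproduce. The end of the course also determines when patients with lymphedema may start decongestive therapy. The plan relies on that timing to argue that decongestive therapy does not contaminate the results.

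**Working it through.** **Stretching ceiling.** Both statements concern stretches by the physiotherapist that tension the cord, and both use the 0–10 VAS defined in the plan's description of that scale. The values are 5 and 6, so the difference is 6 − 5 = 1 point. The verbal limits do not settle the matter. Exercises 4 and 7 are tied to moderate pain and Exercise 6 to what the patient tolerates. The only number the plan attaches to moderate pain is 5, in *Description of the intervention*, and *Intervention Group* does not refer back to it.

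**Massage limit.** The sentence follows a paragraph that sets VAS 6 as a maximum for stretching. It says that the VAS 6 provision applies during massage *also*, and it requires tolerable cord tension. Both features point to an intended upper limit with the negative dropped. The printed sentence nevertheless has no negative, and no other numerical pain limit is given for massage. The preceding paragraph still carries an author's note in Spanish saying that a sentence must be rewritten, so this section was not finally edited.

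**Session count.**

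1. Reproducing the plan's own figure: 5 days per week × 3 weeks = 15 sessions. This agrees with the 15 stated under *Description of the intervention* and *Intervention Group*, and with the 15-day treatment mentioned in the latter if days means treatment days.
2. The Workplan figure at the same frequency: 12 ÷ 5 = 2.4 weeks, that is, two weeks and two days. This does not fit a three-week course.
3. Difference in dose: 15 − 12 = 3 sessions, and 1 − 12/15 = 20%.
4. Planned maximum contact time at about 40 minutes per session: 15 × 40 = 600 minutes against 12 × 40 = 480 minutes.

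| Feature | Description of the intervention | Intervention Group | Workplan |
|---|---|---|---|
| Stretching ceiling | VAS 5 | VAS 6 | not stated |
| Massage limit | not stated | VAS 6, negative missing | not stated |
| Sessions | 15 (5 × 3) | 15 | 12 |

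**Can the early-finish rule reconcile 12 with 15?** No. It is an individual recovery criterion with no number attached, whereas the Workplan gives 12 for the selected patients as a group. The documents contain no amendment log that would make either figure superseded.

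**The case against.** The strongest reply is that these are slips in a rough translation whose meaning a careful reader can recover. Much of that is fair.

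- The massage sentence very probably lost a negative, and its context supports the protective reading.
- One point on a self-marked 0–10 line is a small difference, and both sections work with the same idea of moderate, tolerable pain. The adverse-event withdrawal criteria give further protection.
- The sections that describe treatment say 15, the schedule confirms it, and the lone 12 sits in a paragraph about staff roles. The 20% difference therefore describes a reading that is unlikely to be followed.
- The 15-day phrase is not literally a session count. Fifteen calendar days starting on a Monday contain 5 + 5 + 1 = 11 weekdays, so it supports 15 sessions only if it means treatment days.
- The start of decongestive therapy is fixed by its own sentence, which the Workplan figure does not alter.

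What does not stand is the inference that nothing needs changing. The qualitative safeguards do not say whether 5 or 6 applies. A probable typing error that turns a patient-protection limit into its opposite still has to be corrected. The Workplan is current text, and the conflict between 15 and 12 remains even if the 15-day phrase is set aside.

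**Conclusion.** The concern holds. The plan contains two incompatible pain ceilings for stretching, 1 point apart; one massage limit that reads as its reverse; and two planned courses, 15 and 12 sessions, 20% apart in maximum dose.

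This rests on taking treatment days as the natural sense of the 15-day phrase (not essential to the result) and on the stated approximate session length. The doses are planned maxima. Early finish means that the dose delivered will vary by patient.

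The documents do not show that any of these differences would change an outcome, an error rate or an estimate. The case for correction is safety, clear delivery and reproducibility of the treatment. It should be fixed because the instructions are operative and the remedy is cheap.

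**What to change.** 1. *Intervention Group*, scar massage: insert *not*, so that the stated VAS grade is a limit.
2. *Description of the intervention* and *Intervention Group*: state one VAS ceiling for stretching. Use 5, the lower value, unless the clinical team justifies 6. Apply the same value to massage unless the team specifies another. Choosing 5 is a cautious default; the documents do not establish it as the intended value.
3. *Workplan*: change 12 to 15 sessions, described as a maximum subject to the early-finish rule.
4. Because early finish is allowed, record the number of sessions each patient receives. Logging peak VAS per session is optional and is not needed to resolve the inconsistencies.

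The cost is three small text edits and one session count per patient on the treatment record.
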